8.2 Criteria for In-Study Decisions

Not applicable for this study.

8.3 Subject Withdrawal

If a subject wishes to leave the study at any time, they will be permitted to do so. Every reasonable effort will be made by Quotient Sciences to complete a final assessment/discharge procedures. Quotient Sciences will advise the sponsor of the withdrawal of any subject from the study.

Early withdrawal is defined as the date of the decision to withdraw the subject from the study. Subject completion is defined as the date of the last procedure conducted or last contact (ie phone call/visit) for that subject.

If a subject requests to leave the clinical unit earlier than the planned discharge time eg due to unforeseen personal circumstances, but aims to return to the unit to complete the study, this will be documented as a subject self-discharge and a protocol deviation. The subject must complete the planned assessments/discharge procedures before discharge from the clinical unit and will return for the next study period/assessments, as planned.

Subjects will be withdrawn from the study drug(s) for the following reasons:

- Experiencing a serious or severe AE including but not limited to:
 - corrected QT (QTc) interval of >500 msec or increase in QTc interval of >60 msec from baseline (confirmed following a repeat ECG)
 - ALT concentration >3 x the upper limit of the reference range
- Termination of the study
- Upon the subject's request (withdrawal of consent)
- Significant deviation from the protocol
- Concurrent illness or requirement for prohibited medication
- At the discretion of the investigator/sponsor

For the purpose of withdrawal criteria in Parts 1 and 2, baseline will be considered as the pre-dose Day 1 measurement for each part.

8.4 Subject Replacement

No replacement subjects are to be used in this study.

8.5 Stopping Criteria

The study will be halted, and the risk to other subjects evaluated if any of the following criteria are met:

- A serious adverse reaction (ie, a serious adverse event considered at least possibly related to the IMP administration) in one subject.
- Severe non-serious adverse reactions (ie, severe non-serious adverse events considered as, at least possibly related to the IMP administration) in two subjects in the same cohort of the study, independent of within or not within the same system organ class.

Relatedness will be determined by the investigator.

If the study is halted, a temporary halt will be submitted to the Medicines and Healthcare products Regulatory Agency (MHRA) and ethics committee (EC) in the form of a substantial amendment. The study may be resumed or terminated; however, it will not be resumed until a further substantial amendment to resume the study is submitted and approved by MHRA and EC.

The ARSAC Practitioner will also be informed of the temporary halt

8.6 Study Termination

After the start of protocol activities but prior to the commencement of dosing, the study may be terminated by the sponsor and investigator without consultation with the MHRA, EC and ARSAC practitioner or ARSAC. The end of the trial must be notified to the MHRA and EC immediately and at the latest within 15 days after the study is terminated, clearly explaining the reasons. A description of any follow-up measures taken for safety reasons if applicable, will also be provided. The ARSAC Practitioner and ARSAC will also be notified within an appropriate timeframe.

If the study is abandoned prior to commencement of any protocol activities, the Principal Investigator (PI) or sponsor must notify the EC, MHRA, ARSAC practitioner and ARSAC (if ARSAC research application has been submitted or approved) in writing outlining the reasons for abandonment of the trial.

Once exposure to ionising radiation and/or dosing has begun, the study will be completed as planned unless the following criteria are satisfied that require a temporary halt or early termination of the study:

- The occurrence of serious or severe adverse event(s), as defined in Section 8.5, if considered to be related to the IMP, as defined in Section 14.2.
- New information regarding the safety of the IMP that indicates a change in the risk/benefit profile for the compound, such that the risk/benefit is no longer acceptable for subjects participating in the study.
- Significant violation of Good Clinical Practice (GCP) that compromises the ability to achieve the primary study objectives or compromises subject safety.

If any of the above occurs, the study will be terminated if careful review of the overall risk/benefit analysis described in Section 6.4 demonstrates that the assumptions have changed and that the overall balance is no longer acceptable. In these circumstances termination can only take place with the agreement of the investigator and sponsor. The MHRA, EC, ARSAC practitioner and ARSAC will be informed of study termination.

If it becomes necessary to consider termination of the study after dosing has begun, dosing may be suspended pending discussion between the investigator, sponsor and potentially the ARSAC practitioner (where discussion is related to administration of radiation). Dosing will be stopped immediately on safety grounds.

The study may be terminated or suspended at the request of the MHRA or EC.

8.7 Lost to Follow-up

A subject will be considered lost to follow-up if they fail to return for scheduled visits and cannot be contacted by the clinical unit.

If a subject fails to return to the clinical unit for a required study visit:

The clinical unit must attempt to contact the subject and reschedule the missed visit as soon as possible

Before a subject is deemed lost to follow-up, the investigator or designee must make every effort to regain contact with the participant (eg 3 telephone calls on 3 separate occasions and, if necessary, an email or letter to the participant's last known email/postal address). These contact attempts should be documented in the subject's source.

If the subject cannot be contacted, they will be considered lost to follow-up.

8.8 Treatment Allocation

This is an open-label, non-randomised study, therefore a randomisation schedule will not be produced. A treatment allocation list will be produced prior to dosing with IMP, which will dictate the order in which the treatments should be administered to each subject. The treatment allocation list will be retained in the Investigator Site File (ISF).

8.8.1 Subject Numbers

Subject numbers will be allocated on the morning of dosing in Part 1 according to the code 001 to 006 using the lowest number available.

8.8.2 Blinding

This is an open-label, non-randomised study and therefore blinding is not required.

9 Selection of Subjects

Quotient Sciences must have a full medical history from each subject's general practitioner (GP) within the last 12 months, prior to enrolment for the study.

Subjects will be recruited from the Quotient Sciences panel or by direct advertising to the public.

Before subjects are admitted to the clinical unit, The Over Volunteering Prevention System (TOPS) will be checked to ensure that each subject has not participated in a study at another site within at least 3 months of the dosing date.

9.1 Informed Consent

Subjects will be provided with a written explanation of the study at least the day before the screening visit. A physician or nurse will explain to each subject the nature of the study, its purpose, expected duration and the benefits and risks involved in study participation. Subjects will be informed that, for safety reasons, brief details of their involvement in the study may be revealed to other units and companies that carry out clinical studies in the local area. Subjects will then be given the opportunity to ask questions and will be informed of their right to withdraw from the study without prejudice. After this explanation and before entering the study, the subject will voluntarily sign an informed consent form (ICF). Until written consent has been obtained from the subject no study specific procedure or investigation will be performed. If an amendment is made to the participant information sheet (PIS), participants will be re-consented to the most current version of the ICF(s) where appropriate.

9.2 Inclusion Criteria

1. Healthy males
2. Age 30 to 65 years of age
3. Good state of health (mentally and physically) as indicated by a comprehensive clinical assessment (detailed medical history and a complete physical examination), ECG and laboratory investigations (haematology, clinical chemistry and urinalysis)
4. Body weight ≥ 50 kg
5. Body mass index (BMI) of 18.0 to 35.0 kg/m²
6. Must be willing and able to communicate and participate in the whole study

7. Must have regular bowel movements (ie, average stool production of ≥ 1 and ≤ 3 stools per day)
8. Subjects must have participated in Part 1 in order to be eligible for Part 2
9. Must provide written informed consent
10. Must agree to adhere to the contraception requirements defined in Section 9.4.

9.3 Exclusion Criteria

1. Subjects who previously participated in any other investigational study drug trial in which receipt of an investigational study drug occurred within 90 days prior to dosing
2. Subjects who have previously participated in a study where subjects were dosed with KD025 (QSC200311 and QCL117415).
3. Subjects who are study site employees, or immediate family members of a study site or sponsor employee
4. Subjects with pregnant partners
5. History of any drug or alcohol abuse in the past 2 years
6. Regular alcohol consumption in males >21 units per week (1 unit = $\frac{1}{2}$ pint beer, or a 25 mL shot of 40% spirit, 1.5 to 2 Units = 125 mL glass of wine, depending on type)
7. Current smokers and those who have smoked within the last 12 months. A breath carbon monoxide reading of greater than 10 ppm at screening and admission
8. Current users of e-cigarettes and nicotine replacement products and those who have used these products within the last 12 months
9. Radiation exposure, including that from the present study, excluding background radiation but including diagnostic x-rays and other medical exposures, exceeding 5 mSv in the last 12 months or 10 mSv in the last 5 years. No occupationally exposed worker, as defined in the Ionizing Radiation Regulations 2017, shall participate in the study.
10. Subjects who have been enrolled in an ADME/IV microtracer study in the last 12 months
11. Subjects who do not have suitable veins for multiple venepunctures/cannulation as assessed by the investigator or delegate at screening
12. Clinically significant abnormal biochemistry, haematology or urinalysis as judged by the investigator (laboratory parameters are listed in Appendix 1). Subjects with blood platelet count, haemoglobin and red blood cells lower than the reference range will be excluded
13. Confirmed positive drugs of abuse test result (drugs of abuse tests are listed in Appendix 1)
14. Positive hepatitis B surface antigen (HBsAg), hepatitis C virus antibody (HCV Ab) or human immunodeficiency virus (HIV) results
15. Evidence of renal impairment at screening, as indicated by an estimated creatinine clearance (CLcr) of <80 mL/min using the Cockcroft-Gault equation
16. History of clinically significant cardiovascular, renal, hepatic, chronic respiratory or GI disease, neurological or psychiatric disorder, as judged by the investigator
17. Subject has a history or presence of any of the following:
 - Active GI disease requiring therapy
 - Hepatic disease and/or ALT or AST $>$ ULN
 - Renal disease and/or serum creatinine $>$ ULN
 - Other condition known to interfere with the absorption, distribution, metabolism or excretion of drugs
18. Subject has QT interval corrected using Fridericia's formula (QTcF) intervals >450 msec at screening or admission
19. Serious adverse reaction or serious hypersensitivity to any drug or the formulation excipients

20. Presence or history of clinically significant allergy requiring treatment, as judged by the investigator. Hayfever is allowed unless it is active
21. Donation or loss of greater than 400 mL of blood within the previous 3 months
22. Subjects who are taking, or have taken, any prescribed or over-the-counter drug (other than 4 g of paracetamol per day) or herbal remedies in the 14 days before IMP administration (See Section 11.2). Exceptions may apply on a case by case basis, if considered not to interfere with the objectives of the study, as agreed by the PI and sponsor's medical monitor.
23. Failure to satisfy the investigator of fitness to participate for any other reason

Exclusion criteria 7, 13, 18, 21, 22 and 23 from the list above will be re-assessed at admission/pre-dose for Part 1 and 2.

Healthy subjects who do not meet the inclusion/exclusion criteria for a study should not be enrolled into the study without exception.

9.4 Contraception

Male subjects who are sexually active with a partner of child bearing potential must use, with their partner, a condom plus an approved method of effective contraception from the time of informed consent until 90 days after study discharge. The following methods are acceptable:

- Partner's use of combined (oestrogen and progestogen-containing) hormonal contraception associated with inhibition of ovulation:
 - oral
 - intravaginal
 - transdermal
- Partner's use of progestogen-only hormonal contraception:
 - oral
 - injectable/implantable
 - intrauterine hormone-releasing system
- Partner's use of implantable intrauterine device
- Surgical sterilisation (for example, vasectomy or partner's bilateral tubal occlusion)
- Partner's use of female cap or diaphragm (double barrier)

Alternatively, true abstinence is acceptable when it is in line with the subject's preferred and usual lifestyle. If a subject is usually not sexually active but becomes active, they, with their partner, must comply with the contraceptive requirements detailed above.

These contraception requirements are aligned with guidance issued by the Heads of Medicines Agency: Clinical Trials Facilitation Group [14].

9.4.1 Exposure to Partners During the Study

There is a significant risk of drug exposure through the ejaculate (which also applies to vasectomised males) that might be harmful to the sexual partners (both male and female). Therefore, a condom should be used by all male subjects throughout the study and for 90 days after study discharge.

9.4.2 Sperm Donation

Male subjects should not donate sperm for the duration of the study and for at least 90 days after study discharge.

9.5 Pregnancy

Subjects will be instructed that if their partner becomes pregnant during the study this should be reported to the investigator. The investigator should also be notified of pregnancy occurring during the study but confirmed after completion of the study. In the event that a subject's partner is subsequently found to be pregnant after the subject is included in the study, then consent will be sought from the partner and, if granted, any pregnancy will be followed and the status of mother and/or child will be reported to the sponsor after delivery.

A pregnancy notification form and follow-up will be completed.

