Formal rat and rabbit embryo-foetal developmental toxicology studies with KD025 demonstrated potential for embryo-foetal toxicity and/or malformations at clinically relevant exposures. Therefore subjects with pregnant partners will be excluded from this study.

The purpose of this study is to investigate the oral pharmacokinetics (PK), intravenous (IV) PK, mass balance recovery and metabolite profiling and identification of ¹⁴C-KD025. It is therefore an advantage to enrol a relatively homogeneous population and to minimise variability. Based on the above considerations and target population, healthy male subjects, aged 30 to 65 years are considered suitable for this study.

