10.3.5 Follow-up

A follow-up phone call will take place 5 to 7 days after discharge/after the final collection period to ensure the ongoing wellbeing of the subjects. If a subject reports any AEs which can present a cause for concern, they will be required to attend the clinic for a further follow-up assessment (as an unscheduled visit). Completion of the last follow-up call or unscheduled follow-up visit will be considered the end of the study.

11 Dosing of Subjects

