18.6 Declaration of the End of the Study

The definition of the end of the study is defined as the last visit of the last subject (eg follow-up phone call). Any changes to this definition will be notified as a substantial amendment (see Section 17.1).

The EC and MHRA should be notified in writing of the conclusion of the study within 90 days of the end of the study, or within 15 days if the study is terminated early, clearly explaining the reasons for the termination.

ARSAC and the ARSAC Practitioner will also be notified of the end of trial or early termination of the trial in writing within an appropriate timeframe.

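### The Section 9.5 instruction to report a partner pregnancy stops at the end of the study, although the contraception period runs to 90 days after study discharge

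*Protocol*

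**What the plan says.** Three parts of the protocol bear on this. The SAP does not address partner pregnancy.

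**Reporting (Section 9.5).** Two sentences create a duty to notify. The first is addressed to subjects: "Subjects will be instructed that if their partner becomes pregnant during the study this should be reported to the investigator". The second deals with late confirmation: "The investigator should also be notified of pregnancy occurring during the study but confirmed after completion of the study". A third sentence has no end date. It opens "In the event that a subject's partner is subsequently found to be pregnant after the subject is included in the study" and then provides for partner consent, follow-up of the pregnancy and reporting of the outcome to the sponsor.

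**End of study (Sections 10.3.5 and 18.6).** Section 10.3.5 states: "A follow-up phone call will take place 5 to 7 days after discharge/after the final collection period". It goes on: "Completion of the last follow-up call or unscheduled follow-up visit will be considered the end of the study". Section 18.6 agrees, putting the end at the last subject's last visit and giving the phone call as the example.

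**Precautions (Sections 9.4, 9.4.1 and 9.4.2).** Contraception runs from informed consent to 90 days after study discharge. Section 9.4.1 states that "a condom should be used by all male subjects throughout the study and for 90 days after study discharge", and 9.4.2 bars sperm donation for at least as long. The reason in 9.4.1 is that partners may be exposed to drug in semen. Section 6.3 adds that the animal embryo-foetal studies "demonstrated potential for embryo-foetal toxicity and/or malformations at clinically relevant exposures".

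**The concern.** The protocol sets a period in which it wants conception prevented, and a shorter one in which the subject is asked to report a pregnancy. A conception 30 days after clinic discharge would fall well inside the first and, on the ordinary schedule, outside the second.

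No contact is scheduled after the follow-up call. From then on, the site would normally learn of a pregnancy only if the subject or partner volunteered it. Routine adverse event collection does not help, because Section 14.3 also stops it at that call. At stake is whether the sponsor hears of a pregnancy conceived while its own precautions still applied, in a programme with a stated embryo-foetal hazard. This is a matter of safety reporting and touches neither bioavailability nor mass balance.

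**Working it through.** The plan gives no figure of its own to reproduce. The check is a comparison of wording followed by date arithmetic.

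**Step 1: can the phrase *during the study* include the 90 days?** No. Sections 9.4.1 and 9.4.2 name the study and the 90 days as separate, successive periods. Section 9.5 itself contrasts a pregnancy occurring in the study with one confirmed after completion. Its second sentence therefore extends the date of confirmation, not the date of conception.

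**Step 2: inputs.**
- Clinic discharge to follow-up call, d: 5 to 7 days (10.3.5)
- Precaution period after study discharge: 90 days (9.4 to 9.4.2)
- Planned Part 2 discharge: Day 8, extendable to Day 10 (8.1.2)

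**Step 3: days with no instruction to report, if study discharge means clinic discharge.** Gap = 90 − d.
- d = 5: 90 − 5 = 85 days; 85/90 = 94.4%
- d = 7: 90 − 7 = 83 days; 83/90 = 92.2%

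On the study calendar, discharge on Day 8 puts the call on Day 13 to 15 and the end of the precautions on Day 98: 98 − 13 = 85 and 98 − 15 = 83. Discharge on Day 10 moves every date by two days (Day 15 to 17, and Day 100) and leaves the gap unchanged.

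**Step 4: if study discharge means the follow-up call.** Section 14.3 places discharge from the study at that call. The 90 days then start where the reporting duty ends, so the gap is all 90 days.

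**Step 5: what can shorten the Step 3 figure.** If home collections or an unscheduled visit delay the end of study by h days, the gap is 90 − d − h. The documents give no maximum for h. To close the gap, h would have to reach 83 to 85 days. The synopsis puts the whole interval from screening to the call at about 8 weeks (56 days), so the plan does not foresee a delay of that size.

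**Step 6: does the third sentence of 9.5 close the gap?** It says what happens once a pregnancy is known. It does not ask the subject to make it known.

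**The case against.** The strongest counter-argument is the third sentence of 9.5. It sets no end date, applies to any partner pregnancy found after the subject is included, and is followed by a requirement to complete a notification form and follow-up. Section 14.4.1 counts a congenital anomaly as a serious adverse event, and Section 16.1 contemplates expedited reporting of post-study serious events that the sponsor judges to be SUSARs.

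This disposes of a stronger reading. A reader might infer that a pregnancy conceived after the call would not be followed to outcome, or that there is no surveillance at all. The documents do not support that: a pregnancy that becomes known is provided for, whenever it was conceived. What remains is the trigger. Each of these provisions works only if someone tells the site.

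Two further points stand in part.
- The 92% to 94% is a share of calendar days. It says nothing about how drug exposure or the chance of conception is spread over them. Six subjects receive two single 200 mg oral doses and one 100 µg infusion, under mandatory precautions, so few if any events would be expected. That limits the consequence but does not explain why the two periods differ.
- The participant information and Section 16.3.1 on reporting serious adverse events are not in the text available here and may say more. The point is therefore confined to Section 9.5, which should agree with them in any case.

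**Conclusion.** The point holds as a mismatch between two periods in the protocol. Both notification sentences in 9.5 end with the study, while the precautions in 9.4 to 9.4.2 run to 90 days after study discharge.

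The uncovered part is about 83 to 85 of 90 days if study discharge is clinic discharge and the call takes place on the ordinary schedule. It is shorter by any delay from home collections or an unscheduled visit, and it is all 90 days if study discharge is the follow-up call. Which figure applies depends on a term the protocol does not define consistently.

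The finding concerns the subject's instruction to report, not the follow-up of pregnancies already known. It changes no estimate or analysis. It deserves correction because the hazard and the 90-day period are the sponsor's own and the remedy is a change of wording.

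**What to change.** 1. In both notification sentences of Section 9.5, replace the limit to the study with: 'from informed consent until the end of the contraception period in Section 9.4'. Keep the provision for pregnancies confirmed later, so that a conception within the period counts even if it is recognised after it.
2. Define *study discharge* once and use that definition in 9.4, 9.4.1, 9.4.2 and 14.3. The sponsor must decide which event it denotes.
3. Remind subjects of the reporting duty at the follow-up call, and put the same wording in the participant information.

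The start should be informed consent, as in 9.4. Starting at first dose would drop conceptions between consent and dosing. The pregnant-partner exclusion (criterion 4) is not among those that Section 9.3 lists for re-assessment at admission, so that list would not pick them up.

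The cost is wording in the protocol and participant information. If the latter changes through a substantial amendment, Section 17.1 requires enrolled subjects to be re-consented. There is no added visit, test or analysis. The small downside is that the site must accept notifications after the end-of-study declaration.
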